5. Known to be living with HIV (i.e., enrolled in a treatment program), or consent to HIV testing to confirm HIV status.

VI.D.2. Exclusion Criteria

1. Have positive pregnancy test or report to be pregnant at the time of visit or less than 6 weeks post-partum (will be asked to make an appointment 6 or more weeks post-partum)
2. Report to be menstruating at the time of visit (will be asked to make new appointment)
3. History of hysterectomy and no longer have a cervix
4. History of treatment for cervical abnormalities after cervical screening
5. History of cervical cancer
6. Report no previous sexual activity
7. Because this study has age-specific enrollment goals for WLWH and HIV[-] women, once those enrollment goals are met for each study group, the respective cohorts will be closed and other eligible women will be excluded.

VI.E. Recruitment and Eligibility Screener

During the period of recruitment at a health clinic, WLWH and HIV[-] women will be solicited using advertisements throughout the entire clinic as well as outreach using community health workers (**Figure 1**). In addition, WLWH who are attending routine appointments at the HIV clinics will learn about the study during the group study overview sessions held in the health education room. All women who are interested in the study will meet with a study nurse who will give them an informational flyer and provide a brief verbal description of the study. The

study nurse will help the woman complete the eligibility screener that includes criteria listed above. If eligible and interested, the woman will register for an enrollment visit.

[figure not shown]

Figure 1. Participant recruitment

VI.F. Study Visits

VI.F.1. Enrollment Visit

VI.F.1.a. Informed Consent, HIV testing and Study Questionnaire

As outlined in **Figure 2**, at the enrollment visit conducted in a private exam room, the study nurse will describe the details of the study verbally and women will be provided an opportunity to ask any questions. The participant eligibility will be verified using the eligibility form. Women who report menstruating at the time of visit will be asked to make a new appointment 2 weeks later. Women who report to be pregnant or less than 6 weeks post-partum will be asked to make an appointment 6 or more weeks post-partum.

[figure not shown]

Figure 2. Enrollment visit procedures

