Dry anal and cervicovaginal specimens will be processed and tested using the Atila Ampfire HPV genotyping. Upon arrival, the oral rinse specimen containers will be stored at 4°C refrigerators for processing the next working lab day. Dry brushes and associated labels will be stored in a box in the freezer at -20°C for processing the next working lab day. After testing, residual specimens will be aliquoted and stored frozen at -20°C for further testing.

[figure not shown]
HPV genotyping will be conducted within 2 months of collection to allow ample time to schedule the 6-12 month follow up visit for women who test HPV positive for any HPV type at any tissue site.

VI.F.2. Follow-Up Visit of the HPV-Positive Cohort

Participants who test positive for any of the 17 HPV types on their cervicovaginal, oral, and/or anal specimen collected at baseline will be scheduled for a 6-12 month follow-up visit with a window of 5-15 months after their baseline visit; participants who test negative on all three specimens will exit the study. Objectives of the follow-up visit are to 1) measure 6-12 month HPV persistence, an accepted primary endpoint in prophylactic HPV vaccine trials (89), and 2) ensure the safety of the participants. As outlined in **Figure 3**, at the follow-up visit, the participant's eligibility status will be confirmed. Participants will provide a urine sample for pregnancy testing to confirm they are not pregnant. Counseling will be provided pre and post testing as needed. Participants unknown to be living with HIV will have a rapid HIV test with pre- and post-HIV-testing counseling following the National Rapid HIV Diagnostic Testing Protocol. Any participant who tests positive will be referred to the health center's HIV clinic for

HIV management following the Ministry of Health's HIV management guidelines. Only specimens from those anatomic sites that were HPV positive at baseline will be collected utilizing the same protocol as at enrollment. A study staff will transport the oral saline rinse and dry swabs to the study lab to be stored until study testing for 17 HPV genotypes; the follow-up cervicovaginal and anal specimens will be tested within one month to ensure timely follow-up of high-risk individuals who need diagnostic services (colposcopy and/or anoscopy).

Figure 3. Activities at follow-up visit

VI.G. Study Test Results and Clinical Management

VI.G.1. Management of Persistent Cervicovaginal HPV

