Similarly, exploratory analyses will compare the effectiveness of HPV vaccination for cross-protection types and endpoints of cumulative detection of Gardasil®-targeted HPV types-associated CIN2+ and/or anal intraepithelial neoplasia grade 2 or more severe (AIN2+) (vs. untargeted HPV type-associated CIN2+ and/or AIN2+) between study groups.

For participants in the existing IeDEA database we will extract HIV specific variables. For those who we cannot match to the IeDEA database, will extract HIV specific variables from medical records.

In another exploratory analysis, among WLWH, the presumed route of HIV acquisition (either maternal to child or behavioral) will be compared with HPV positivity and, among HPV-positive women, HPV viral load.

VII.A.2. Sample Size/Power for Gardasil®-vaccinated vs. unvaccinated WLWH.

For this analysis, we will make the following assumptions: 1) at least 30% prevalence of HPV infection (of any anatomic site) at baseline, 25% of which will be Gardasil®-target HPV types and 55% will be untargeted HPV types, 2) a 10% loss to follow-up (LTFU) in at follow up visit, and 3) at least 70% of HPV infections persist for 6-12 months. We justify an HPV prevalence of at least 30% based on 30% prevalence of high-risk HPV infection of the cervix in 30-year-old WLWH from our previous U54 study (109). We expect that the HPV prevalence may be higher since the prevalence of HPV, like that of other sexually transmitted infections, tends to peak about 5 years after the median age of sexual initiation in a population. However, we conservatively used 30% to ensure adequate statistical power. We justify our assumption of a maximum of 10% follow-up, given our experience working in Rwanda over the last ~20 years. We justify 70% of prevalent HPV infections persisting for 6-12 months, given that 36-50% of prevalent HPV infections persist 6-months in HIV[-] women (109, 110) and WLWH have an impaired immunity to HPV (8, 9).

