Study data will be stored in REDCap and maintained on password protected study computers behind the institution firewall. REDCap is a secure, web-based application designed to support data capture for research studies providing: 1), an intuitive interface for validated data entry; 2) audit trails for tracking data manipulation and export procedures; 3) automated export procedures for seamless data downloads to common statistical packages; and 4) procedures for importing data from external sources. REDCap is hosted on a secure server and has undergone a Governance Risk & Compliance Assessment by All REDCap electronic data files shared with Albert Einstein College of Medicine will be maintained by the HIPAA-compliant Epidemiology Study Management and Informatics Core Facility (ESMI) at Einstein. The Albert Einstein College of Medicine policy on use of REDCap can be found at:
http://ric.einstein.yu.edu/ric_files/REDCap%20Appropriate%20Use%20Policy.pdf

Side effects/adverse events due to ablative treatments are generally minor (pain, cramping, and watery discharge). Any pain, bleeding, or stress that might occur related to colposcopy, biopsies, vaginal collections, and/or LEEP are typically modest and no greater than those risk for the primarily HIV[-] women in the general population for whom cervical screening is recommended by the WHO and most countries in the world. These side effects and serious adverse events will be managed through referral to the Gynecology department at RMH. As needed, consults with other medical specialists will be sought. Care for study-related adverse events will be paid for by the study. Serious adverse events will be reported to the IRBs.

Study nurses have been trained in pre- and post-counseling for HIV testing and will provide support to participants taking rapid HIV tests. They will be trained to assist participants with any anxiety or discomfort experienced through responses to questionnaires and/or testing HPV positive.

Although women who are pregnant are at very low risk of adverse events due to the enrollment and follow-up procedures in this study, it is important to avoid any potential perceived risk. For this reason, all participants will have a pregnancy test performed at all visits. If they are found to be pregnant, they will be exited from the study and invited to enroll when they are at least 6 weeks post-partum.

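### The pregnancy exit rule also applies at the follow-up visit, so it gives up persistence outcomes that a deferred visit could recover, and the plan does not say how these exits are handled or counted

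*Combined protocol and SAP*

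**What the plan says.** Section X.B.2 (Protections Against Risk) states that "all participants will have a pregnancy test performed at all visits", and it says of women with a positive test that "they will be exited from the study and invited to enroll when they are at least 6 weeks post-partum". The reason given there is to avoid perceived risk. The same paragraph rates the actual risk to pregnant women from the enrollment and follow-up procedures as very low.

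Section VI.F.2 confirms that the rule reaches follow-up: eligibility is checked again at that visit, and a urine pregnancy test is required. Specimen collection is described after this step. Follow-up is for women positive at baseline, since "participants who test negative on all three specimens will exit the study", and each positive woman "will be scheduled for a 6-12 month follow-up visit with a window of 5-15 months after their baseline visit". The section gives the visit two objectives, measuring persistence and ensuring participant safety.

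At enrollment the plan defers rather than exits. The exclusion in VI.D.2 reads "Have positive pregnancy test or report to be pregnant at the time of visit or less than 6 weeks post-partum", and the woman is asked to book a later appointment.

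Section VII.A.2 assumes "a 10% loss to follow-up (LTFU) in at follow up visit". It justifies this as a maximum based on about 20 years of experience in Rwanda. Section IX.E repeats 90% retention. Neither mentions pregnancy.

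**The concern.** Persistence is a main outcome (VI.A) and the endpoint behind the 757 per group (VII.A.2). It needs a second specimen. A woman exited on a positive pregnancy test, before specimens are taken, has no persistence result, and no text provides for obtaining one later. Some of these results could be recovered, because the window runs to 15 months and the plan already defers visits for pregnancy at enrollment.

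The invitation to enroll afterwards raises a second question. No eligibility criterion excludes an earlier participant, and no rule says whether a returning woman keeps her PID or which baseline is analysed. Nearly all such women would be known HPV-positives, so a second baseline record would be neither independent nor typical. (VI.I.1 also allows some women who are AmpFire-negative but positive on the quality-control test to be referred for follow-up.)

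Finally, the cohort is aged 18-28, so pregnancy is a foreseeable reason for a missing outcome. The plan does not say whether the 10% allows for it, and Section VII gives no method for missing outcomes.

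**Working it through.** **Inputs from VII.A.2:** 757 women per group; 30% HPV-positive; 25% of infections targeted and 55% untargeted; 10% loss; 70% persistence; significance level 0.05 (taken as two-sided); effect 0.5. **Assumed here, because the documents give no figure:** 5% or 10% of women attending follow-up are pregnant, these exits come on top of the 10%, a pregnancy lasts 9 months, and 6 weeks is 1.4 months.

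**1. The plan's own figure.** Persistent targeted or untargeted infections per group = 757 × 0.30 × 0.90 × 0.70 × (0.25 + 0.55) = 114.5. The targeted share among unvaccinated women = 0.25/0.80 = 31.25%. Power comes from the normal approximation for two proportions, pooled variance under the null and no continuity correction: Φ{[|p1 − p2|√n − 1.96√(2p̄(1 − p̄))] / √(p1(1 − p1) + p2(1 − p2))}.

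- With 0.5 as a ratio of shares (31.25% against 15.6%), power is 80.1%. The required n is 115 infections, or 115/0.1512 = 761 women per group, close to 757. Of the variants tried, only this one uses every stated input and comes within 3% of 757.
- With 0.5 as a true odds ratio (31.25% against 18.5%), power is 60.7%. That is a separate matter, but it means the base figure has no reserve under either reading.

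**2. Adding pregnancy exits.** Total loss = 1 − 0.9 × (1 − p). Women due at follow-up = 757 × 0.30 = 227 per group, and 227 × 0.9 = 204 are expected to attend.

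| Pregnant among attendees (assumed) | Total loss | Women exited per group | Infections per group | Power, ratio of shares | Women per group for 80% | Power, true OR 0.5 |
|---|---|---|---|---|---|---|
| 0% | 10% | 0 | 114.5 | 80.1% | 761 | 60.7% |
| 5% | 14.5% | 10 | 108.7 | 78.0% | 801 | 58.5% |
| 10% | 19% | 20 | 103.0 | 75.8% | 845 | 56.2% |

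**3. What deferral recovers.** A woman who conceives c months after baseline reaches 6 weeks post-partum at c + 9 + 1.4 months. This is within 15 months if c ≤ 15 − 10.4 = 4.6. Later conceptions carried to term still give a missing outcome.

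**4. How many could have a second baseline.** A woman not pregnant at enrollment who carries to term cannot return before about 10.4 months. With recruitment of 14-16 months (XIII), only those enrolled in the first 14 − 10.4 = 3.6 or 16 − 10.4 = 5.6 months could do so, which is 26% or 35% under even accrual. Applied to 10-20 exits, this gives about 3-7 women per group. If 70% were still positive, baseline prevalence would move from 30% to between (227.1 + 0.7 × 2.6)/(757 + 2.6) = 30.1% and (227.1 + 0.7 × 7.2)/(757 + 7.2) = 30.4%. Cohort closure (VI.D.2) and the age limit of 28 lower this further. A pregnancy that ends early, or a recruitment overrun, would raise it.

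**The case against.** A reader might infer that the plan counts the same women twice. The documents do not say so. VI.F.1.a describes one unique PID for all forms and specimens, and the invitation to enroll also fits a woman found pregnant at the enrollment visit, since consent and PID assignment precede the test there. The consent form and visit figures are not available and might cover re-enrollment. What stands is a gap: no rule prevents a second record, but the effect is small.

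A reader might also infer that pregnancy is left out of the 10%. The plan lists no components of that figure and calls it a maximum. Its silence does not show exclusion, so the power losses above depend on the assumption that these exits are additional.

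A third tempting reading is that unequal pregnancy rates across age groups bias the vaccine comparison. VII.A.1 bases its relative measure on targeted against untargeted types within each group, precisely because the groups differ in age and exposure. Exits unrelated to HPV type leave that ratio unchanged, and the documents give no reason why they should depend on type. The plain comparisons of prevalence between groups in the same section lack that protection, but the documents offer nothing from which to size an effect.

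The precision cost is also modest. The 30% and 70% inputs are stated as floors, and a prevalence of 0.30/0.90 = 33.3% would fully offset 10% exits. Nor does the plan say that an exited woman's baseline data are discarded; only her persistence result goes unmeasured.

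None of this changes the effect of the rule as written: an outcome that could still be collected in the window is given up.

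**Conclusion.** The point holds in a limited form. The exit rule applies at the only visit that measures persistence, so following it loses main-endpoint results, including some that a post-partum visit within 15 months would supply. The main cost is precision: about 2 points of power at 5% exits and about 4 at 10%, from a base of 80.1%. This rests on an assumed pregnancy rate, on exits being additional to the 10%, and on 0.5 being a ratio of shares. Duplicate baselines are a gap in the rules that might affect a few women per group. The documents do not support a claim of actual double counting, of known exclusion from the 10%, or of bias in the targeted-to-untargeted ratio. This is a cheap improvement and not a flaw that threatens the study's conclusions.

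**What to change.** For women found pregnant at follow-up, replace exit and re-enrollment with retention under the original PID and baseline. Defer the research visit, as is already done at enrollment. Use the persistence result if the visit falls within 5-15 months, and otherwise count it as missing. State that each woman contributes one baseline record. In VII.A.2, say whether the 10% includes pregnancy losses, restate the figure if it does not, and report these losses by study group.

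X.B.2 should also be reconciled with the safety objective of the follow-up visit in VI.F.2, because the documents describe no further route for a woman exited with a positive HPV result. No clinical rule is proposed here.

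The cost is protocol and data-handling wording and some later visits, with no new procedures. Only part of the outcomes would be recovered, because term pregnancies conceived more than about 4.6 months after baseline run past the window.

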APPENDIX III. ENROLLMENT QUESTIONNAIRE

Thank you for agreeing to participate in our study. This interview should take no more than 20 minutes. Some of these questions are personal about your life, your reproductive health, and your sexual history. All your answers are strictly confidential, and it is very important for us that you try to answer all the questions as openly as possible, even if they are a little uncomfortable or embarrassing. This information will be important in understanding how the HPV vaccine protects women against HPV infection. If you don't understand any of the questions, please inform the study nurse who will try to help explain them. You should also be aware that you have a right not to respond to any question with which you are uncomfortable.

A. Socio-demographics

1. What is your date of birth? DD/ MM /YYYY (enter all 0 if not remembered)

__ / __ / __ __

2. What is your age? __ (Year)

3. What is your marital status?

- Married/Cohabiting
- Divorced
- Widowed
- Separated
- Single
- Choose not to answer

4. Do you live in Kigali?

- Yes
- No (Skip to Question #6)
- Choose not to answer (Skip to Question #6)

5. In what area in Kigali City Province do you live?

- Nyarugenge
- Kicukiro
- Gasabo urban (e.g., Kacyiru, Kimironko, Kinyinya, etc.) Gasabo rural (e.g., Nduba, Jabana, Gikomero, etc.)
- Do not know

Choose not to answer

6. Who do you live with? (Check all that apply)

- Live alone
- Partner/spouse
- Daughter(s)/son(s)
- Parents and/or other family
- Other: _____

7. What is your primary occupation?

- Student
- Employed by government, another institution, or company
- Self-employed (Small and medium enterprises)
- Self-employed (High income earnings)
- Unemployed/Do not work
- Other (specify): _____
- Choose not to answer (Skip to Question #8)

The following questions are sensitive and personal in nature. Your answers will be kept confidential. You may choose not to answer certain questions. Answering any question is voluntary

B. Parity

8. What age did you have your first full term birth ? __ (Year) (Enter 00 if refuse to answer, enter 99 if never pregnant or not yet had a pregnancy that resulted in a full term birth – i.e. all pre-term deliveries) (if 00 or 99, skip to Question #11)

9. How many full term births have you had in your lifetime? _____

10. Have you given birth in the last year?

- Yes
- No
- Choose not to answer

C. Contraceptive Use

11. Have you ever used Jadelle (contraceptive)?

- Never
- No (Skip to Question #13)
- Choose not to answer (Skip to Question #13)

12. Do you currently use Jadell (contraceptive)?

- Yes
- No
- Choose not to answer

13. Have you ever used oral contraceptives?

- Yes
- No (Skip to Question #15)
- Choose not to answer (Skip to Question #15)

14. Do you currently use oral contraceptives?

- Yes
- No
- Choose not to answer

15. Have you ever used Depo Provera (contraceptive)?

- Yes
- No (Skip to Question #17)
- Choose not to answer (Skip to Question #17)

16. Do you currently use Depo Provera (contraceptive)?

- Yes
- No
- Choose not to answer

17. Do use condoms as a contraceptive?

- Yes
- No (skip to Question #19)
- Choose not to answer (skip to Question #19)

18. Have you used condoms as a contraceptive in the last 6 months?

- Yes
- No
- Choose not to answer

19. Have you ever used another contraceptive method?

- Yes. Please specify: _____
- No (skip to Question #21)
- Choose not to answer (skip to Question #21)

20. Do you currently use another contraceptive method?

- Yes. Please specify: _____
- No
- Choose not to answer

D. Sexual Behaviors

This last section of the questionnaire contains questions about sexual practices you may have engaged in over the years. This will help us understand your likelihood of having been exposed to human papillomavirus (HPV).

21. How many men have you had vaginal sex with, in your lifetime until now? Vaginal sex is a man inserting his penis into your vagina.

- No Men (Skip to question #25)
- 1 Man
- 2-3 Men
- 4-5 Men
- 6 or more Men
- Choose not to answer

22. How old were you when you first had vaginal sex? __ (Year) (Enter 00 if refuse to answer)

23. How many men have you had vaginal sex with in the last 6 months?

- No Men (Skip to Question #25)
- 1 Man
- 2 or more Men

Choose not to answer

24. In the past 6 months, how often has he used a condom during vaginal intercourse?

Never
 Occasionally
 Half the time
 Almost always
 Always

25. Have you ever had anal intercourse? Anal intercourse is a man inserting his penis into your anus/rectum.

Yes
 No (Skip to Question #29)
 Choose not to answer (Skip to Question #29)

26. How many men have you had anal sex with, in your lifetime until now?

1 Man
 2-3 Men
 4-5 Men
 6 or more Men
 Choose not to answer

27. How many men have you had anal sex with, in the past 6 months?

No Men (Skip to Question #29)
 1 Man
 2 or more Men
 Choose not to answer

28. In the past 6 months, how often has he used a condom during anal sex?

Never
 Occasionally
 Half the time
 Almost always
 Always

29. Have you ever performed oral sex on a man? (Oral sex would be a blow job or you sucking someone's penis)

- Yes
- No (Skip to Question #32)
- Choose not to answer (Skip to Question #32)

30. In your lifetime until now, how many men have you performed oral sex on until now?

- 1 Man
- 2-3 Men
- 4-5 Men
- 6 or more Men
- Choose not to answer

31. During the past 6 months, how many men have you performed oral sex on?

- No Men
- 1 Man
- 2 or more Men
- Choose not to answer

E. HPV Vaccination History

32. Have you had the HPV vaccine (most women have the vaccine when they are around 11-13 years old)?

- Never vaccinated (End of Questionnaire)
- Vaccinated
- I don't remember (End of Questionnaire)

33. How many times have you had the HPV vaccine?

- One time
- Two times
- Three times
- I don't remember

END OF QUESTIONNAIRE

